For the second objective, data from risk assessment instruments that are already administered will be collected at baseline and follow-up. Since risk assessment with the FARE has to be performed twice per year, this form of data collection is in line with existing procedures and thus will not take up additional time of patient and therapist. For the third objective, therapists will be asked to indicate the number of treatment sessions that the patient participated in. Therapists can retrieve these data from their calendar, the electronic patient file or supported by the office assistants, the exact method depending on their own preference. Data for the fourth objective on engagement will only be collected from patients in the experimental condition. The TWEETS engagement questionnaire will be built into the internet-based intervention to ensure that it is filled out at the right point in the intervention, i.e. at the beginning, halfway and at the end. Another reason for this is that, if engagement is a predictor for effectiveness, Minddistrict will integrate the TWEETS in all interventions. The fifth and sixth objective will be addressed by means of qualitative data, collected by means of semi-structured interviews with patients and via questionnaires with open-ended with therapists. Finally, at baseline, patients are asked to fill out several questions on demographics, including their gender, age, marital and employment status and education level. Participants will also be asked if they received forensic and/or regular psychiatric treatment in the past. Additionally, at baseline therapists will be asked to provide information

about the inpatient clinic in which the patient is treated, the main treatment goal, type of offense, and diagnoses. These data will be used to describe the sample and will be collected via Qualtrics.

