#### ***Treatment readiness – CVTRQ***

Treatment readiness refers to the presence of factors that contribute to engagement with treatment and therapeutic change [12]. This concept is often used in forensic psychiatry and does not only cover motivation and willingness to change, but also responsivity, which refers to the suitability of the treatment program offered. It incorporates internal factors such as personality and cognitive-emotional features of the patient that are related to therapeutic change. Qualitative research has shown that therapists believe that, if used well, internet-based interventions can contribute to treatment readiness because they might fit the needs and wishes of the patient, resulting in better responsivity to treatment. In other words: the use

of internet-based interventions might increase the fit between the treatment and needs of the patient, resulting in higher treatment readiness. Additionally, the patient can gain new insights and skills individually as opposed to because of a therapist, which might contribute positively to their intrinsic motivation and willingness to change [4, 5].

Treatment readiness is assessed by the Dutch version of the Corrections Victoria Treatment Readiness Questionnaire (CVTRQ): a validated self-reported questionnaire [32]. The total scale consists of 20 items, divided into four subscales. The subscale Attitude and Motivation (AM) measures attitudes and beliefs about treatment programs and the desire to change. The scale Emotional reactions (ER) measures emotional responses to the individual's offending behaviour. Offending beliefs (OB) refers to beliefs about personal responsibility for offending behaviour. The subscale Efficacy (EF) measures perceived ability to participate in treatment programs.

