**Step 5: Randomization and start intervention – Week 12**

Directly after the patient has provided informed consent, the patient is randomized by the researcher. This is communicated to the therapist, who will let the patient know whether they will start with the intervention 'Aggression' or if they will participate in the control group.

After the first session of the internet-based intervention is finished, the TWEETS will be administered to participants in the experimental group via the Minddistrict platform, because the TWEETS is integrated in the intervention.

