### ***Research objective 4: Engagement***

To investigate whether engagement predicts effectiveness, simple linear regression analyses will be run for three variables: regulatory emotional self-efficacy, treatment readiness, and aggression. The score on the TWEETS on T0, T1 and T2 will be used as independent variables in three different regression analyses. The change scores (i.e. difference between scores on T2 and T0, and the difference between scores on T3 and T0) for all relevant variables (self-efficacy, treatment readiness and aggression) will be used as dependent variables for two regression analyses. These scores will be added in a second analysis to

measure whether it adds predictive value on the dependent variables. Furthermore, in order to investigate if the TWEETS scores predict adherence, three analyses with the TWEETS score on T0 and T1 as dependent variables are run, this time with the number of finished lessons of the intervention as dependent variable.

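### Objective 4 regresses raw change on engagement without the T0 score, so an engagement–baseline correlation can create or mask an association

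*Combined protocol and SAP*

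**What the plan says.** Section 10.2, Research objective 4, states that "simple linear regression analyses will be run for three variables: regulatory emotional self-efficacy, treatment readiness, and aggression". On the predictor it says: "The score on the TWEETS on T0, T1 and T2 will be used as independent variables in three different regression analyses". The dependent variables are "The change scores (i.e. difference between scores on T2 and T0, and the difference between scores on T3 and T0) for all relevant variables". No covariate is named.

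A further sentence, beginning "These scores will be added in a second analysis to", is about added predictive value. The scores it refers to can only be the TWEETS scores or the change scores just mentioned. Nothing in it points to the T0 score of the outcome questionnaire.

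Three other places matter:

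- Section 8.1: "Data for the fourth objective on engagement will only be collected from patients in the experimental condition".
- Section 8.3, Step 5: "After the first session of the internet-based intervention is finished, the TWEETS will be administered to participants in the experimental group". The first TWEETS therefore comes after the T0 outcome questionnaires.
- Sections 3.3 and 8.3, Step 4: all three outcome questionnaires are completed at T0, so the covariate is already collected.

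**The concern.** A change score contains the T0 score with a negative sign. When the slope of follow-up on T0 is below 1, patients who start high tend to change downwards and patients who start low tend to change upwards, whatever their engagement. If engagement is correlated with the T0 score, a regression of change on engagement alone picks up part of this pattern. The spurious association has the opposite sign to the TWEETS–T0 correlation.

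Such a correlation is plausible for at least one outcome. Section 8.1.1 says "Treatment readiness refers to the presence of factors that contribute to engagement with treatment and therapeutic change", and section 8.1.2 describes TWEETS as covering perceived usefulness for behaviour change and for reaching one's goals. Randomisation gives no protection, because engagement is observed within one arm.

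The result has a use. Section 8.1 says that the platform provider will build the TWEETS into all its interventions if engagement proves to predict effectiveness. A masked association, or one with the wrong sign, would misinform that decision.

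**Working it through.** **The plan's own figure.** Section 4.4 gives 64 patients per condition. A two-sided two-sample t-test with d = 0.5, 80% power and 5% significance needs 63.77, rounded up to 64, so the figure reproduces. No sample size is given for objective 4. I take n = 64 as the experimental-arm size; the recruitment goal of 154 gives 154/2 = 77 if the split is equal.

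**Assumptions, none given in the documents.** T0 and follow-up scores are standardised with equal variances. Let r be the T0–follow-up correlation (here also the slope of follow-up on T0) and p the TWEETS–T0 correlation. Engagement is unrelated to follow-up given T0. Significance is 0.05 (section 10.1), taken as two-sided.

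**Bias.**

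- Spurious slope of change on TWEETS: −(1 − r)p
- Spurious correlation: −p√((1 − r)/2)

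For r = 0.5, p = 0.3: slope −0.5 × 0.3 = −0.15; correlation −0.3 × √0.25 = −0.15. By Fisher's z with n = 64, atanh(0.15) × √61 = 1.18, and the rejection rate is Φ(1.18 − 1.96) + Φ(−1.18 − 1.96) ≈ 22%.

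Simulated false-positive rates of the planned regression (20,000 replicates, n = 64):

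| r | p = 0 | p = 0.1 | p = 0.3 | p = 0.5 |
|---|---|---|---|---|
| 0.3 | 4.8% | 7.4% | 29.2% | 66.8% |
| 0.5 | 4.7% | 6.9% | 21.9% | 52.4% |
| 0.7 | 5.1% | 6.1% | 15.0% | 33.9% |
| 0.9 | 5.1% | 5.3% | 8.2% | 14.4% |

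With T0 as covariate, the rate is 4.7% to 5.4% in all sixteen cells.

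**Dependence on n.** At r = 0.5, p = 0.3, Fisher's z gives about 26% with n = 77. The end TWEETS follows the final lesson (section 8.3, Step 7), and section 1 reports that most patients do not complete all lessons, so fewer patients will supply it. If 30 did (an assumption), the rate at r = 0.5, p = 0.3 would be about 12%. The spurious slope itself does not shrink with n.

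**Masking.** If engagement has a true slope b given T0, and follow-up has slope r on T0 given engagement, the planned regression estimates b − (1 − r)p. With r = 0.5 and p = 0.3, a true slope of 0.15 SD per SD gives 0.15 − 0.15 = 0.

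**Precision.** With engagement unrelated to T0, residual variance (adjusted over change score) is (1 + r)/2, that is 0.65, 0.75, 0.85 and 0.95 for r = 0.3, 0.5, 0.7 and 0.9. The variance ratio for the engagement slope also depends on p:

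[(1 − r²)/(1 − p²)] / [2(1 − r)(1 − p²(1 − r)/2)]

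| r | p = 0 | p = 0.3 | p = 0.5 |
|---|---|---|---|
| 0.3 | 0.65 | 0.74 | 0.95 |
| 0.5 | 0.75 | 0.84 | 1.07 |
| 0.7 | 0.85 | 0.95 | 1.18 |
| 0.9 | 0.95 | 1.05 | 1.28 |

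Values above 1 mean that the adjusted slope is the less precise one.

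**The case against.** **The link is not established.** The readiness definition concerns engagement with treatment, whereas the TWEETS measures engagement with the digital intervention. No correlation is reported for any of the three outcomes. This stands: the existence and size of p are assumptions, and the evidence is thinnest for self-efficacy and aggression.

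**It is partly a choice of question.** Whether engaged patients change more is a legitimate descriptive question, and section 2 asks only whether engagement is a predictor. Moreover, if engagement tracks a stable trait that the questionnaires measure with error, the change-score slope can be unbiased and the T0-adjusted slope is not. This stands too. The plan justifies neither model, which is a reason to report both and not to drop the change-score regression.

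**Stronger readings that the documents do not support.**

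- A reader might infer that any engagement–baseline link distorts the result. Bias also needs a follow-up-on-T0 slope different from 1, and with p = 0.1 and r of 0.5 to 0.7 the false-positive rate is only 6% to 7%.
- A reader might infer that omitting T0 always costs precision. It raises residual variance, but for the engagement slope the comparison reverses when the link is strong, as the last table shows.
- A reader might infer from the T2 label in Table 1 and section 10.2 that the end TWEETS is taken at the same time as the T2 outcomes and cannot be used to predict them. Sections 8.1 and 8.3 (Step 7) tie it to finishing the final lesson. Section 3.3 puts that at 11 weeks for patients on schedule and T2 at 14 weeks after baseline, so it comes about three weeks earlier for them. A general restriction on which TWEETS scores to use is not warranted on this ground.

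**Conclusion.** The point holds in conditional form. Objective 4 uses raw change scores with no T0 covariate, and the second analysis, as worded, does not supply one. If engagement is correlated with T0 and the follow-up-on-T0 slope is below 1, the planned slope is shifted by −(1 − r)p. At r = 0.5 and n = 64, false positives run from about 7% (p = 0.1) to 52% (p = 0.5). They are about 5% if p is zero, and lower than these figures for the end TWEETS if few patients supply it. These figures assume no engagement effect given T0, and values of r and p that the documents do not provide.

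The issue is confined to a secondary analysis within the experimental arm. The mixed-model group comparison for objective 1 (section 10.1) is untouched. T0 adjustment would not make the engagement result causal.

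**What to change.** In section 10.2, objective 4:

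1. Make the main analysis a regression of the T2 (or T3) score on TWEETS, with the T0 score of the same questionnaire as covariate.
2. Keep the change-score regression as a sensitivity analysis, and comment if the two disagree.
3. State which scores enter the second analysis, and in which model.
4. Say that the result is read as an association.

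The cost is a few sentences in the analysis section. The T0 scores are already collected, and no visit, questionnaire or sample-size change is needed.

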### **10.3 Other study parameter(s)**

#### ***Research objective 5 & 6: Patient and therapist perspective***

To explore reasons for the effectiveness or ineffectiveness of the internet-based intervention Aggression according to forensic psychiatric patients and therapists, qualitative data will be collected. Anonymized transcripts will be created of these data. These transcripts will be analysed via an inductive approach, using the method of constant comparison [47]. First, relevant fragments will be extracted from the anonymized transcripts. Based on these fragments, two researchers will create an initial version of a coding scheme, one per research question. These coding schemes will contain main and subcodes and a first version of a definition for each code. These coding schemes will be applied to five transcripts by two researchers. After discussion amongst both coders, the coding scheme will be updated to ensure that it optimally fits the data. After that, both researchers will again code five transcripts and discuss whether any further changes are necessary. This process continues up until all transcripts are coded and the coding scheme covers all fragments. Intercoder reliability will be calculated, with a goal of at least 80% agreement.

## **11. ETHICAL CONSIDERATIONS**

### **11.1 Regulation statement**

The study will be conducted according to the principles of the Declaration of Helsinki 2013 (World Medical Association, 2013) and in accordance with the Medical Research Involving Human Subjects Act (WMO).

### **11.2 Recruitment and consent**

The principal investigator is primarily responsible for recruitment of participants. Recruitment will take place in the four participating organizations and will start in April 2022. In order to ensure the feasibility of the study, researchers will actively work together with staff of Transfore, De Woenselse Poort, Kairos and GGZ Noord-Holland Noord. First, patients are informed about the study in a very general sense by their healthcare provider, after which they are asked if they consent to be contacted by a researcher. The researcher will contact the patient by the preferred means of communication – i.e. phone, e-mail or videoconferencing - and will fully inform them about the goal and nature of participating in the study. After this initial contact, the patient will have five days to consider participation, during which they are encouraged to contact the researcher if they have any remaining questions. After five days, the patient is contacted again by the researcher and is asked if they want to participate and if so, if they want to sign the informed consent form. The role of the researcher in this process is a deliberate choice to avoid any potential role conflicts. Patients might feel that their treatment progress can be affected by the decision to (not) participate, which might result in a situation in which they do not feel free to decline a request for participation from their therapist. To prevent this, informed consent is always asked by the researcher. Additionally, it is clearly communicated to the patient by both the therapist and researcher that participation does not affect their treatment progress in any way. Furthermore, it is made clear to potential participants that they can drop out of the study at any moment, without giving a reason for this. Communication about these conditions is done verbally and via the information folder that patients will receive from their therapist. To summarize, multiple precautions are taken to ensure that the patient does not feel forced in any way to participate in this study, and that the decision to participate is made on a voluntary basis.

### **11.3 Objection by minors or incapacitated subjects (if applicable)**

Not applicable.

## **11.4 Benefits and risks assessment, group relatedness**

### **11.4.1 Benefits for patients, therapists and forensic mental healthcare**

For participants in the experimental condition, the main advantage can be that they can follow a potentially effective intervention that can provide them with more skills to effectively deal with their aggression regulation problems. Explorative, qualitative research has shown that these internet-based interventions can have multiple potential benefits for patients, such as receiving more information and exercises on their disorder(s) or behaviour compared to TAU, an accompanying increase of knowledge and skills to deal with their problems, and an increased sense of ownership and accounting improvements to themselves instead of the therapist due to working on a part of their treatment independently [19, 21]. A tangible benefit for all participants – also those in the control condition - is that they are compensated with two vouchers of a total of €20 to compensate for their invested time and effort.

A more abstract, indirect benefit – especially relevant for participating therapists - is that this study can contribute to better forensic mental healthcare. The importance of this study is illustrated by a recent study amongst Dutch forensic mental healthcare professionals, which clearly showed the need for more robust evaluation studies of eHealth interventions [19]. Especially considering the fact that internet-based interventions have been present in Dutch forensic mental healthcare for about ten years, is quite surprising that their effectiveness has not been studied yet. Consequently, it is essential to study the effectiveness of these modules, especially in a domain in which evidence-based practice is a core value. If the web-based interventions prove to be effective, this can be an additional impulse for implementation in clinical practice. In that way, these modules provide an effective way to provide additional care to vulnerable patients, which might reduce the overall changes of recidivism and quality of care. In line with this, the effectiveness of these interventions might provide an additional impulse for implementation, since professionals working in forensic mental healthcare indicate that the absence of evidence is one of the experienced implementation barriers [19, 21]. If this study shows no proof for effectiveness, this should be a starting point for a broader discussion in forensic mental healthcare: is it worthwhile to invest much time, money and other resources in the implementation of these modules, or should these resources be focused on other, more promising technological additions to care? In any case, this study will contribute to evidence-based practice and thus the most optimal form of treatment for forensic psychiatric outpatients.

### **11.4.2 Risk assessment**

As mentioned before, the web-based intervention Aggression has been used since 2012. No adverse effects have been reported by any of the organizations that have been using the module Aggression and other comparable interventions to developer Minddistrict.

Furthermore, qualitative research in the Dutch forensic field via questionnaires and interviews has also shown no negative consequences of these modules [19]. A potential negative consequence that was mentioned was that working on self-reflection exercises might result in an excessive amount of negative feelings in patients [21]. While this can be therapeutic, a negative consequence might be that patients are not able to successfully manage these emotions. However, all exercises and texts in the Aggression intervention are developed by psychologists, in collaboration with experienced therapists to prevent these types of issues. Furthermore, the intervention is used in a blended way, which means that therapists regularly monitor how the patient is doing and can address unhelpful negative feelings and identify ways to deal with these. Finally, throughout all the years that these types of interventions have been used, no observable negative consequences of independently working on these modules have been identified.

The control group of this study will not receive the Aggression intervention, or any other type of internet-based intervention, during the data collection period. After that, these interventions can be used, which will be clearly communicated. Not following these interventions is not expected to have a negative impact on the quality of treatment of the participants in the control condition. First of all, at this point in time, it is not yet clear whether internet-based interventions Aggression actually result in better treatment outcomes in Dutch forensic mental healthcare. This means that participants in the control condition are not denied evidence-based care, simply because these interventions are not evidence-based yet. Furthermore, research with log data and interviews has shown that at this point, many patients do not have access to internet-based interventions at all, mostly because their therapist does not introduce these modules. To specify: one study showed that only 54% of all therapists working at an organization used the modules, of which the largest part used it with very few patients [21]. This implies that the use of internet-based interventions is not a part of standard care yet, meaning that participants in the control condition are not denied standard care procedures.

To summarize: in order to be able to deliver high-quality, evidence-based care, it is essential to investigate whether internet-based interventions that have been used for several years are indeed effective.

### **11.5 Compensation for injury**

The University of Twente has a liability insurance which is in accordance with article 7 of the WMO. However, since there are no risk associated with the study, the University of Twente has asked for an exemption of the liability insurance in accordance with article 7 of the WMO.

### **11.6 Incentives (if applicable)**

Participants in both groups will receive a total amount of €20 for their participation, of which €10 will be provided at T1, and €10 after completing the follow-up measurement (T3). An accompanying risk regarding the ecological validity of these results is that patients might complete the intervention due to the financial reward, even though they might not want to work on the intervention anymore. This is accounted for in multiple ways. First, it will be made clear that the financial reward is dependent on completing the questionnaires, and not the internet-based intervention. Patients thus can stop using the intervention, but can still receive the financial compensation if they complete all questionnaires. Second, adherence to these interventions in 'real life' is an important topic. In order to account for this, another study that is out of scope of this proposal will be conducted to determine the adherence to these types of interventions outside of a study context. By means of log data, insight will be gained into the way these interventions are used in clinical practice. These analyses will be conducted before this RCT is completed, which allows the researchers to use these findings on adherence from the 'real world' and compare them to the adherence of the participants in this study. Third, in line with this, researchers will account for problems with ecological validity in this study when interpreting these results.

